Comparison Between Ultra Sound Guided Rectus Sheath Block and Field Block for Midline Hernia Repair

NCT03225313

Start Date 20th August 2017

Investigators:

1. [name]

a. Other Investigators	[name]. [name].
	[name] [name]. [name] [name]. [name] [name]. [name]
c. Department name	Anesthesia Department.

Background and Rationale:

Pain is a complex but an important protective phenomenon. It may be defined as an unpleasant sensory and emotional experience associated with actual or potential tissue damage or described in terms of such damage (1). Good operative analgesia reduces the stress response to surgery, which is very important for patients with compromised cardiovascular respiratory functions (1). Good postoperative pain relief is important as it alleviates patient's distress and helps in rapid uncomplicated recovery (1).

Field block achieved by wound infiltration is a method of postoperative analysis commonly used alone or as a part of multimodal analysis regimens (2). It was developed to improve postoperative analysis, reduce opioid consumption and

hasten patient recovery .The use of local anesthetics (LAs) instead of opioid minimizes opioid adverse reactions, reduces nursing work, decreases resting pain, pain on motion, and thus allows better patient mobility (2). Field block carries the risk of wound infection and some surgeons oppose its use.

A rectus sheath block can provide effective pain relief for umbilical or other midline surgical incisions by blocking the intercostals nerves. It can be done using the landmark technique but it carries the risk of puncturing the posterior rectus sheath, peritoneum and bowel (3).

Use of ultrasound technology for rectus sheath block has reduced this risk considerably (3). Ultrasound guidance for regional anesthesia is associated with higher block success rates, shorter onset times, and reduced total anesthetic dose required and reduced complications. There is also the advantage of direct observation of pattern of anesthetic spread (4).

Objectives:

To compare between Ultra-sound guided rectus sheath block VS Field block infiltration in providing a good analgesia for patients undergoing midline hernia repair to detect which one is superior.

Study Design:

Prospective randomized double blinded controlled clinical trial will be done with a total number of 75 patients will be divided into 3 groups.

Ethics Committee approval (was it ethically approved by the department):

This protocol has been approved by the Ethics Committee at Theodor Bilharz Research Institute.

Study Methods:

Population of study & disease condition:

> 75 patients(ASA I or II) undergoing midline hernia repair under general anesthesia will be recruited and will be randomly allocated using a computer generated randomization table (research randomizer, https://www.randomizer.org). The allocation was kept in brown sealed envelopes.

- > Control group.
- > Field block infilteration group.
- ➤ Ultra sound Guided Rectus sheath block group.

Inclusion criteria:

- 1. Elective midline hernia repair surgery.
- 2. Age: adult patients between 18 60 years old.
- 3. Gender: Both male and female.
- 4. ASA Class: I & II.

Exclusion criteria:

- 1. Refusal of patient.
- 2. Pregnancy and lactation.
- 3. Fever or sepsis.
- 4. Patients ASA III or IV.
- 5. Renal impairment.
- 6. Addicts and drug abusers.

- 7. Patients taking corticosteroids or any cardio active drugs.
- 8. Local infection at site of the injection.
- 9. Allergy to any of the study medications.

Methodology in details:

Anesthesia technique:

✓ Preoperative :

- During the pre-operative period visual analog scale (VAS) for pain assessment from 0 to 10, with 0 meaning no pain and 10 meaning the worst pain imaginable will be explained to patients.
- 30 minute before surgery, IV 20 G cannula will be inserted in each patient forearm to collect 5 ml venous blood as preoperative sample for estimation of the level of cortisol and catecholamine.

✓ Monitoring:

In theatre, a five-lead ECG, non-invasive blood pressure, pulse oximetry, end-tidal carbon dioxide and neuromuscular monitoring (Infinity Kappa, Dräger, Lübeck, Germany). Bi-spectral (BIS) module (Infinity® BISxTM SmartPod®, smoothing rate: 15 or 30 seconds, software revision: VF5) was attached to the patients' forehead for the depth of anaesthesia monitoring using disposable BIS electrodes (BIS Quatro, Aspect Medical Systems, USA) after proper skin preparation, were attached to the patient

✓ Induction and maintenance

- During mask preoxygenation, patients baseline hemodynamic parameters will be recorded regarding blood pressure, heart rate.
- General anesthesia will be standardized for all patients with:

2 μg kg⁻¹ fentanyl and 2 mg kg⁻¹ propofol. Neuromuscular blockade will be achieved with 0.5 mg kg⁻¹ atracurium followed by tracheal intubation.

Muscle relaxation will be maintained by 0.1mg/kg/30 minute of Atracrurium.

- Mechanical ventilation will be adjusted with fresh gas flow oxygen in air 30-50% at a rate of 1 L min⁻¹to maintain end-tidal carbon dioxide of 35-40 mm Hg and Spo2 greater than 94%.
- BIS values will be maintained between 40 and 60.
- All surgical procedures will be done in the range between 10 am and 1 pm and by the same surgical team.
- Patients hemodynamic parameters regarding blood pressure and heart rate will be recorded every 2.5 minutes.
- Core temperature will be measured using an esophageal thermometer and normothermia will be maintained using a forced air warming blanket and actively warmed infused solution.
- Patients will receive ringer solution infusion at a rate 2 5 ml / kg / hour.
- Patients were randomly allocated to one of three groups namely the control group (Group C), the field block group (Group FB), or the RSB group (Group RSB) according to a computer generated randomization table (research randomizer, https://www.randomizer.org). Patients in the Field block group received a sham bilateral RSB using a total volume of 0.3ml. kg⁻¹ of normal

saline plus a field block using 0.3ml. kg⁻¹ of 0.5% bupivacaine. The RSB group received a bilateral RSB using a total volume of 0.3ml. kg⁻¹ of 0.5 % bupivacaine plus a sham field block using 0.3 ml. kg⁻¹ of normal saline. The control group received 0.3 ml. kg⁻¹ of normal saline for each block. A colleague not participating in the trial prepared the syringes that were used for the blocks. The patients, the anaesthetist administering the blocks, and colleagues collecting the postoperative observations were not aware of group allocation or injectate composition.

- An increase in HR and/or MAP > 25 % of baseline values will be treated by IV fentanyl 0.5 μg kg⁻¹ boluses & the total fentanyl dose will be recorded. Atropine 0.5 mg increments will be used to control bradycardia (<50 beat min⁻¹) while hypotension (less than 20% of preanesthetic level) will be managed by increasing fluid infusion rate or decreasing inhalational anesthetic concentration.
- Reversal of neuromuscular blockade will be achieved by intravenous administration of neostigmine 0.05 mg kg⁻¹ and atropine 0.02 mg kg⁻¹.
- Patients will be extubated and transferred to post- anesthetic care unit.
- Postoperatively, pain was controlled using morphine PCA, paracetamol 1 gm intravenously every 6 hours and Diclofenac intravenously every 12 hours.
- VAS will be recorded immediately post-operative, after 2, 4 and 6 hours.
- Time to first analgesia requirement will be recorded and 24 hour postoperative morphine consumption will be recorded.
- Nausea and vomiting will be recorded immediately postoperative using a categorical scoring system (0 = none, 1 = nausea, 2 = retching, 3 = vomiting).
 Ondansteron 4 8 mg i.v will be given for patients with score 2.

Research Template 6 Final Version: 14/11/2011

• Pa	atients will be discharged out after sco	ring 12 points or more according to Fast
tra	ack discharge score (5) as follows:	
>	Level of consciousness	Score
	Awake and oriented	2
	Arousal with minimal stimulation	1
	Responsive only to tactile stimulation	n 0
>	Physical activity	
	Able to move all extremities on	
	command	2
	Some weakness in movement of	
	extremities	1
	Unable to voluntarily move extremiti	ies 0
>	Hemodynamic stability	
	Blood pressure less than 15% of baseline	
	MAP value	2
	Blood pressure 15%–30% of baseline	
	MAP value	1
	Blood pressure more than 30% below	
	baseline MAP value	0
>	Respiratory stability	
	Able to breathe deeply	2
	Tachypnea with good cough	1
	Dyspneic with weak cough	0
>	Oxygen saturation status Maintains value more than 90% on	

	noom oir	2
	room air	2
	Requires supplemental oxygen (nasal	
	prongs)	1
	Saturation less than 90% with	
	supplemental oxygen	0
>	Postoperative pain assessment	
	None or mild discomfort	2
	Moderate to severe pain controlled with	
	IV analgesics	1
	Persistent severe pain	0
>	Postoperative emetic symptoms	
	None or mild nausea with no active	
	vomiting	2
	Transient vomiting or retching	1
	Persistent moderate to severe nausea	
	and vomiting	0
Total sco	ore 14	

Total Score 14

Sampling:

Patients in the three groups will undergo blood sampling for measurement of cortisol and catecholamine level using ELISA technique 3 times :

- 30 min. pre –op.
- 1 hour after the start of the procedure.

- 2 hour after the end of the procedure.
- 6 hours after the end of the procedure

Pain assessment:

Pain score to surgery will be assessed according to the VAS pain score sheet as follows:

- Immediately after the admission to recovery room.
- 15 minutes following the admission to recovery room.
- 2 hours after the end of the procedure.
- 6 hours after the end of the procedure.
- Time to 1st analgesia request.
- 24 hour post operative analgesia requirement.
- Intra-operative fentanyl consumption.

Primary outcomes (Most important outcomes to be assessed):

Assessment of postoperative pain with each technique.

Secondary outcome parameters (other outcomes to be assessed) :

- Assessment of stress response with each technique through measuring cortisol and catecholamine levels.
- Hemodynamic Parameters regarding blood pressure and heart rate.
- Incidence of nausea and vomiting post operative.

- Modified Aldrete score.
- Time to hospital discharge.

STATISTICAL METHODS:

Sample size calculation was done using the comparison of postoperative pain score between RSB, local infiltration and control groups as it was the primary outcome of our study. As reported in previous publication (6,7) the mean \pm S.D. of postoperative pain score in RSB group was 4.65 ± 2.1 , while in local infiltration group it was 5.45 ± 1.9 and in control group it was 7.1 ± 1.1 . We calculated that a sample size of 23 in each group will be able to detect a one unit difference between the groups with 80% power at $\alpha = 0.05$ level using analysis of variance test (one way ANOVA test) for independent samples. The sample size calculation was done using the G*Power© software (Institut für Experimentelle Psychologie, Heinrich Heine Universität, Düsseldorf, Germany) version 3.1.9.2. To allow for drop-outs, 25 patients in each group were recruited.

The statistical analysis was performed using IBM SPSS® Statistics version 22 (IBM® Corp., Armonk, NY, USA). Numerical data were expressed as mean and standard deviation or median and range as appropriate. The qualitative data were expressed as frequency and percentage. The relation between qualitative variables was examined using either Pearson's Chi-square test or Fisher's exact test.

The quantitative continuous data were tested for normality using the Kolmogorov-Smirnov test and the Shapiro-Wilk test. The comparisons between the three groups were done using either analysis of variance (ANOVA) for normally distributed quantitative variables or Kruskal-Wallis test (non-parametric ANOVA) for none-normally distributed data then post-hoc test" was used for pair-wise comparison. ANOVA with repeated measures (for normally distributed data) or Friedman test (non-parametric ANOVA with repeated measures for non- normally distributed data) was used to compare more than two consecutive measures of numerical variables

followed by post hoc tests for pairwise comparisons of repeated readings. Due to multiple comparisons, the p-value was corrected using the Bonferroni method.

The time to first analgesia request analysis was done using the Kaplan-Meier method and comparison between groups was done using the log-rank test. The Coxregression method was used to calculate the hazard ratio (HR) for risk estimation with its 95% confidence interval (CI). All tests were two-tailed. A p-value < 0.05 was considered significant.

Source of funding:

Will be provided by Theodor Bilharz Research Institute.

Time plan:

Starting date: August 2017.

References:

- 1. Merskey H. Classification of chronic pain: description of chronic pain syndromes and definitions of pain terms. Monograph for the subcommittee on Taxonomy International Association for the study of pam. Pain Suppl Vol 3. Amsterdam: Elsevier Science 1986.
- 4. Sites BD and Brull R. Ultrasound guidance in peripheral regional anesthesia: philosophy, evidence-based medicine, and techniques. Current Opinion in

Anesthesiology; 19: 630-9. 2006.

- 5. Paul F. White. New Criteria for Fast-Tracking After Outpatient Anesthesia: A Comparison with the Modified Aldrete's Scoring System. Anesth Analgesia criteria for fast tracking;88:1069–72. 1999.
- 6. Charlton S GJ. Cochrane Database of Systematic Reviews Perioperative transversus abdominis plane (TAP) blocks for analgesia after abdominal surgery (Review) Perioperative transversus abdominis plane (TAP) blocks for analgesia after abdominal surgery (Review). Cochrane Database Syst Rev Art. 2010;(12):1–59.
- 7. Flack SH, Martin LD, Walker BJ et al. Flack abstract. Available from: http://www2.pedsanesthesia.org/meetings/2011winter/syllabus/submissions/abstract s/wapd/GA30.pdf.

Research Template 12 Final Version: 14/11/2011

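### Hernia type is open at entry, no stratification is described and no analysis uses a baseline factor; recording and prespecifying type would be a cheap precision gain, of a size the documents cannot fix

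*Combined protocol and SAP*

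**What the plan says.** - **Eligibility.** The surgical requirement under Inclusion criteria is "Elective midline hernia repair surgery". Neither the inclusion nor the exclusion list restricts hernia type, size or recurrence. The Background says a rectus sheath block can give "effective pain relief for umbilical or other midline surgical incisions".
- **Allocation.** Under Population of study, patients "will be randomly allocated using a computer generated randomization table", kept in sealed envelopes. Under Induction and maintenance, allocation is again "according to a computer generated randomization table". Neither place mentions strata, blocks or minimization. The Study Design gives a "total number of 75 patients will be divided into 3 groups".
- **Analysis.** Under Statistical Methods the trial is sized with an "analysis of variance test (one way ANOVA test) for independent samples". Groups are then compared by ANOVA or Kruskal-Wallis with post-hoc pairs. Repeated readings use repeated-measures ANOVA or Friedman. Time to first request uses Kaplan-Meier, log-rank and Cox. No baseline factor is named in any of these.
- **Variation already controlled.** General anaesthesia is standardized, and surgery is done between 10 am and 1 pm and "by the same surgical team".
- **Data recorded.** Hernia type is not listed as a variable to be collected.

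**The concern.** The protocol holds the surgical team, time of day and anaesthetic constant but leaves the operation open to any midline hernia. If a larger or incisional repair hurts more than a small umbilical one, that difference adds to the residual variance of the pain score, and possibly of morphine use and time to first request. By chance it may also fall unevenly across three arms of 25. The objective is to find which of two active blocks is superior, and that is the contrast with least power to spare. If type is never recorded, nobody can later check whether an apparent difference between blocks reflects case mix.

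**Working it through.** **Inputs from Statistical Methods.** Three groups; 23 per group for 80% power at alpha 0.05; 25 per group recruited; one-unit target; planning SDs 2.1 (rectus sheath block), 1.9 (local infiltration) and 1.1 (control).

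**Assumptions, not in the documents.** A share p = 0.3 to 0.5 of patients has the larger or incisional type. That type shifts VAS by d = 0.5 to 2 units. Total SD is 2.1 in every arm.

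**Step 1: the plan's own figure.** For a one-way ANOVA, f = SD of the group means / error SD, and the noncentrality is λ = f² × N. With means one unit apart (0, 1, 2) and error SD 2.1, f = 0.8165 / 2.1 = 0.389. For N = 69, λ = 10.43 and power is 81.4%; 22 per group gives 79.5%. So 23 is reproduced, under a reading of the one-unit difference that the protocol does not spell out.

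**Step 2: baseline for the block-versus-block contrast.** With 25 per arm, the standard error of a difference is 2.1 × √(2/25) = 0.594. Power for one unit from the noncentral t (48 df) is 37.8%.

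**Step 3: variance due to hernia type.** The between-type variance is p(1−p)d². Its share of the total is R² = p(1−p)d² / 4.41. The residual SD after adjustment is √(4.41 − p(1−p)d²). Adjusted overall power uses λ/(1−R²) with one error degree of freedom fewer. Adjusted pairwise power uses the residual SD, also with one fewer.

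| d (VAS units) | R² (p = 0.3 to 0.5) | Residual SD | Overall power, 23 per group | Block-vs-block power, 25 per arm |
|---|---|---|---|---|
| 0 (unadjusted) | 0 | 2.10 | 81.4% | 37.8% |
| 0.5 | 1.2-1.4% | 2.09 | 81.8-81.9% | 38.2-38.3% |
| 1 | 4.8-5.7% | 2.05-2.04 | 83.3-83.7% | 39.4-39.7% |
| 1.5 | 10.7-12.8% | 1.98-1.96 | 85.8-86.6% | 41.5-42.3% |
| 2 | 19.0-22.7% | 1.89-1.85 | 89.1-90.5% | 45.0-46.6% |

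Worked case, p = 0.5 and d = 1.5: 0.25 × 2.25 = 0.5625; 0.5625 / 4.41 = 12.8%; √(4.41 − 0.5625) = 1.96. In patient terms, 75/(1−R²) − 75 is about 9 to 11 patients at d = 1.5, and about 4 to 5 at d = 1.

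**Step 4: chance imbalance.** If the number of larger-type patients in each arm is binomial with n = 25, two given arms differ by 5 or more with probability 16% (p = 0.3) or 20% (p = 0.5). At d = 1.5, a gap of 5 moves the difference by 1.5 × 5/25 = 0.3 units. Over repeated randomizations the shift has SD d × √(2p(1−p)/25) = 0.19 to 0.21 units.

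**Step 5: is that shift extra error?** No. It is already part of the 0.594 in Step 2. Adjusting at d = 1.5 lowers the standard error to 0.555-0.561, a reduction of 0.03 to 0.04 units.

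**The case against.** The strongest reply is that the premise is not in the documents. They do not say that hernia type affects pain, that incisional hernias will be enrolled, or in what proportion. The Background phrase "umbilical or other midline surgical incisions" describes what the block can cover, not who will be recruited. This stands, so the effect must be labelled as assumed.

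The upper effects also sit awkwardly with the planning SDs. Against the control SD of 1.1 (variance 1.21), a 1.5-unit effect would take 39-46% of the variance (0.4725/1.21 to 0.5625/1.21), and a 2-unit effect 69-83% (0.84/1.21 to 1.00/1.21). Those SDs come from other publications, so this does not exclude such effects, but it makes the top of the range doubtful. Every patient also has morphine PCA, paracetamol and diclofenac, which may move an effect of surgical extent from VAS into morphine use.

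Simple randomization with an unadjusted test is a legitimate design, and age, sex and ASA class are unstratified too. This also stands, and it limits the point to an improvement.

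Three stronger readings are tempting. A reader might infer that the omission biases the comparison or inflates type I error. It does not: randomization protects both, and the standard error already carries the imbalance. A reader might infer that one-way ANOVA is the only pain analysis. The sentence naming it concerns sample size, and the analysis text also offers Kruskal-Wallis, repeated-measures ANOVA and Friedman. Finally, the protocol never states that allocation is unstratified; that is inferred from silence in two places.

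**Conclusion.** The point holds as a low-cost precision improvement. Type is unrestricted, no stratification is described, and no between-group analysis uses a baseline factor. Under the assumed case mix and SD 2.1, the gain is under one power point at 0.5 units, about 2 points at 1 unit, and about 4 to 5 points at 1.5 units, for both the overall test and the block-versus-block contrast. If type has no effect on pain, the gain is nil and one degree of freedom is lost.

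It would be wrong to infer that adjustment makes the block-versus-block comparison adequately powered. Even at the doubtful 2-unit effect, power for one unit stays below 47%. The documents also do not support calling hernia type an established pain driver in this trial.

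**What to change.** 1. Record hernia type (primary umbilical/epigastric or incisional) before randomization, and state the allocation method in full.
2. If allocation is not yet fixed, use one permuted-block list per type, each with its own envelopes. The protocol mixes future and past tense, so this may no longer be open; if so, skip to step 3.
3. In either case, prespecify type as a factor in the linear model for VAS and morphine. Kruskal-Wallis and Friedman cannot take a second factor, so on the non-parametric branch name a stratified rank test (such as van Elteren) or a rank-based ANCOVA. Stratify the log-rank and Cox analyses by type.

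**Cost.** One baseline field, one degree of freedom, a second envelope set if stratified, and arm sizes that may differ slightly from exactly 25. No extra patients or procedures are needed.

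### No pre-operative VAS is scheduled and the primary pain comparison has no covariate: a cheap chance of extra precision, its size dependent on a correlation the documents do not give

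*Combined protocol and SAP*

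**What the plan says.** All references are to the combined protocol and SAP.

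- **Methodology in details, Preoperative.** The 0 to 10 scale is introduced to the patient: "0 meaning no pain and 10 meaning the worst pain imaginable will be explained to patients". Nothing asks for a score to be written down at that contact.
- **Methodology in details, postoperative items.** "VAS will be recorded immediately post-operative, after 2, 4 and 6 hours".
- **Pain assessment.** A second list begins "Immediately after the admission to recovery room" and continues with 15 minutes, 2 hours and 6 hours. Every time in both lists is after surgery.
- **Primary outcomes.** "Assessment of postoperative pain with each technique". No time point is named.
- **Statistical methods.** "The comparisons between the three groups were done using either analysis of variance (ANOVA) for normally distributed quantitative variables or Kruskal-Wallis test". Serial readings are handled by repeated-measures ANOVA or Friedman, which "was used to compare more than two consecutive measures of numerical variables". No covariate is named for any outcome. Multiple comparisons are Bonferroni-corrected.
- **Baselines that are taken.** Cortisol and catecholamine are sampled 30 minutes before surgery, and blood pressure and heart rate are recorded before induction. All are secondary outcomes.

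**The concern.** Pain is the primary outcome, yet it is the one main measurement without a pre-operative value, although staff are already with the patient explaining the scale. A score taken before allocation cannot be affected by treatment, so adjusting for it does not bias a randomised comparison. If it predicts postoperative pain, it narrows the interval.

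Precision matters here because the stated objective is to find out which of the two blocks is better, and that pairwise comparison is weakly powered. A baseline score would also show how the arms compared on pain before surgery. With 25 per arm, the standard error of a between-arm difference in any baseline variable is √(2/25) = 0.28 of its SD. A pre-operative score cannot be recovered once the patient has had surgery.

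**Working it through.** **Inputs from the Statistical methods section.** Postoperative pain "in RSB group was 4.65 ± 2.1 , while in local infiltration group it was 5.45 ± 1.9"; control 7.1, SD 1.1; 23 per group for 80% power at 0.05 by one-way ANOVA to detect one unit; 25 per group recruited; two-tailed tests at 0.05; Bonferroni correction.

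**Assumptions.** r is not in the documents, so the range 0 to 0.5 is shown. It is taken as the same in both arms. The Bonferroni level is taken as 0.05/3 = 0.0167, for three pairwise comparisons.

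**Step 1: the plan's own figure.** The 23 per group can be reproduced with three means in one-unit steps (0, 1, 2) and the largest quoted SD, 2.1:

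- SD of the means = √(2/3) = 0.816, so f = 0.816/2.1 = 0.389.
- Noncentral F with noncentrality N·f²: power is 79.5% at 22 per group and 81.4% at 23.

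So 23 per group corresponds to a two-unit spread across the three arms, and it assumes no covariate. Adding a useless covariate (r = 0) costs one degree of freedom, and power goes from 81.40% to 81.37%.

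**Step 2: rectus sheath block versus field block, unadjusted.** SE = √(2.1²/25 + 1.9²/25) = √(8.02/25) = 0.566. For one unit, Welch power is 40.9% at 0.05 and 24.8% at 0.0167.

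**Step 3: with adjustment.** ANCOVA on a baseline with correlation r multiplies the residual SD by √(1 − r²). The equivalent sample size per arm is 25/(1 − r²). Both SDs are scaled by √(1 − r²) and Step 2 is repeated. The lost degree of freedom is ignored, as Step 1 shows it is negligible.

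| r | √(1 − r²) | CI narrower by | 25 per arm acts like | Power, 1 unit, 0.05 | Power, 1 unit, 0.05/3 |
|---|---|---|---|---|---|
| 0 | 1.000 | 0% | 25.0 | 40.9% | 24.8% |
| 0.1 | 0.995 | 0.5% | 25.3 | 41.3% | 25.1% |
| 0.2 | 0.980 | 2.0% | 26.0 | 42.3% | 25.9% |
| 0.3 | 0.954 | 4.6% | 27.5 | 44.2% | 27.5% |
| 0.4 | 0.917 | 8.3% | 29.8 | 47.1% | 30.0% |
| 0.5 | 0.866 | 13.4% | 33.3 | 51.5% | 33.9% |

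**Step 4: the plan's own expected gap.** 5.45 − 4.65 = 0.8. At 0.05, power goes from 28.3% to 29.2% (r = 0.2) or 35.9% (r = 0.5).

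**The case against.** The strongest case on the other side has five parts.

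1. **The gain is not demonstrated.** It rests wholly on r. Patients are elective, ASA I or II, with no pre-operative pain requirement. If many score 0, the covariate has little spread. Nor would it capture how a person uses the scale, since anyone without pain marks 0. Postoperative pain is also treated with patient-controlled morphine plus scheduled paracetamol and diclofenac, which may weaken the correlation. This stands. A reader might infer that the plan is definitely discarding precision, or that these patients differ widely in pain before surgery; the documents support neither statement.
2. **Validity is untouched.** The unadjusted comparison of randomised, blinded arms is unbiased, chance imbalance is already covered by the test's error rate, and the sample size does not rely on adjustment. This stands, so no bias should be read into the omission.
3. **The missing score is not the reason the analysis is unadjusted.** Cortisol, catecholamine, blood pressure and heart rate have baselines and are not adjusted either. Recording a VAS would change nothing unless ANCOVA is also specified. This stands, and the fix asks for both.
4. **The power shortfall comes from the sample size.** This stands: even r = 0.5 leaves power at 52%, or 34% after Bonferroni.
5. **One model term is not a complete fix.** Kruskal-Wallis takes no covariate, and without a primary time point ANCOVA has no defined response. This stands, and the fix covers both.

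None of this defeats the suggestion. If r is near zero, the statistical cost is one degree of freedom.

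**Conclusion.** The point holds as a cheap improvement to efficiency, conditional on r. It is not a defect in validity. The documents establish that no pre-operative VAS is scheduled, that no covariate is named, and that several secondary outcomes do have baselines. They do not establish how much precision is forgone.

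For r from 0 to 0.5, the interval narrows by 0% to 13%. Power for a one-unit difference between the two blocks gains 0 to about 11 percentage points at 0.05 and 0 to about 9 at 0.05/3. The lower part of the range is the relevant one if most patients arrive without pain. These figures rest on the plan's SDs of 2.1 and 1.9, 25 analysed per arm, three Bonferroni-corrected pairs and an assumed r.

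**What to change.** 1. Record one VAS score when the scale is explained, before allocation.
2. Reconcile the two VAS schedules (one has 4 hours, the other 15 minutes) and name one postoperative time point as primary.
3. Pre-specify ANCOVA at that time point, with arm and pre-operative VAS as terms. State that a rank-based ANCOVA replaces it if residuals are clearly non-normal, so that the Kruskal-Wallis route has an adjusted counterpart.
4. Keep the Bonferroni-corrected pairwise contrasts, and report the unadjusted comparison as a sensitivity analysis.

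**Cost.** One extra item on the case report form, one model term and one degree of freedom, with no additional visit or procedure. The gain may turn out to be small, and the low power of the pairwise comparison needs separate attention.

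### The incidence of postoperative nausea and vomiting rests on one score taken immediately after surgery, so symptoms that first appear later are not counted

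*Combined protocol and SAP*

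**What the plan says.** Under Secondary outcome parameters, the protocol lists "Incidence of nausea and vomiting post operative" without a window, a definition of a case or a data source.

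The measurement is described once, in the postoperative part of Methodology in details: "Nausea and vomiting will be recorded immediately postoperative using a categorical scoring system". The scale runs from 0 (none) through nausea and retching to 3 (vomiting).

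Other postoperative measures run longer:

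- Pain is followed to 6 hours: "VAS will be recorded immediately post-operative, after 2, 4 and 6 hours". The separate Pain assessment list has an entry at "15 minutes following the admission to recovery room" in place of the 4-hour one, and it too ends at "6 hours after the end of the procedure".
- Opioid exposure continues after surgery: "Postoperatively, pain was controlled using morphine PCA". It is totalled over a day: "24 hour postoperative morphine consumption will be recorded".

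The only other emetic item is in the fast-track discharge score. Its best category begins "None or mild nausea with no active".

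**The concern.** An incidence counts patients who develop a condition over a stated period. A single score at the start of that period records who has symptoms at that moment. A patient who is well at the immediate score and vomits two hours later counts as having no symptoms. A patient who scores 1 and later vomits stays at 1.

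The mismatch matters here because the protocol's Background says that using local anaesthetic in place of opioid reduces opioid adverse reactions. Emetic symptoms are scored at the start of the postoperative period, while the opioid exposure that might cause them is counted for 24 hours. A published percentage labelled as postoperative incidence would be read as covering much more time than it does.

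**Working it through.** The documents give no figure for nausea and vomiting, so there is none to reproduce. The sample size of 23 per group (25 with drop-outs) was set on the pain score and does not bear on this point. The check is mainly a reading of the text.

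**Step 1: does the immediate term mean a time point or a period?** The pain schedule in the same part of the protocol uses the same term as one entry in a list, separate from 2, 4 and 6 hours. The natural reading for nausea and vomiting is therefore also a time point. No duration is given.

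**Step 2: is a later 0-3 score scheduled anywhere?** No. The pain lists, the blood-sampling list and the 24-hour morphine total do not mention it. No worst-score or cumulative rule is given.

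**Step 3: can the fast-track item fill the gap?** It is untimed, serves to decide discharge and is not linked to the outcome. Its top category puts no symptoms and mild nausea together, so it cannot give an incidence of nausea.

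**Step 4: are later contacts available?** Yes. Contacts at 2 and 6 hours appear in both pain lists and in the Sampling list. The 4-hour and 15-minute entries each appear in only one pain list.

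**Step 5: illustration of size.** All rates and capture shares are assumptions. Take true 0-6 hour rates of 40% (control), 20% and 20% (the two blocks), with 25 per arm:

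25 × 0.40 + 25 × 0.20 + 25 × 0.20 = 10 + 5 + 5 = 20 of 75 patients (26.7%).

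Let the immediate score catch a share c of these cases, equal in every arm. The reported count is 20c and each arm's rate is multiplied by c. Power is by exact enumeration of all 3 × 2 tables at alpha 0.05, for the two tests the Statistical Methods section allows.

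| Capture c | Arm rates | Reported cases | Power, Fisher (three groups) | Power, Pearson chi-square |
|---|---|---|---|---|
| 100% | 40/20/20% | 20 of 75 (26.7%) | 0.320 | 0.352 |
| 75% | 30/15/15% | 15 of 75 (20.0%) | 0.220 | 0.245 |
| 50% | 20/10/10% | 10 of 75 (13.3%) | 0.133 | 0.147 |
| 25% | 10/5/5% | 5 of 75 (6.7%) | 0.053 | 0.075 |

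**Step 6: other assumed base rates.** For two arms of 25, two-sided 0.05, by normal approximation (rough at the smallest counts), power at capture of 100%, 75%, 50% and 25% is:

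- 50% vs 20%: 0.61, 0.44, 0.28, 0.15.
- 30% vs 10%: 0.42, 0.31, 0.21, 0.12.

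The pattern is the same. These figures show what a given loss would do. They do not estimate the loss in this trial.

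**The case against.** The protocol does not say that the score is taken only once, nor that it is the sole source for the incidence outcome. The immediate term could loosely mean the recovery-room stay. The fast-track item could register later retching or vomiting before discharge, because those fall in its lower categories. The illustration assumes its capture share, so falling counts and power follow automatically, and power is low even at full capture. The outcome is one of several secondary ones and was not powered. A 0-6 hour window would itself miss a first symptom at 8 hours.

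Much of this stands. That the score is the sole source is an inference, drawn because no other recording is described. The size is unknown, and the comparison would be weak under either schedule. The fast-track item may pick up some later vomiting, but nothing in the plan carries it into the outcome. The choice between 6 and 24 hours is a judgement that the documents do not settle.

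None of this supplies a reading under which later symptoms are counted. If the recovery-room stay was meant, the text has to say so, and the outcome would still end well before the opioid exposure does.

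**Conclusion.** The concern holds. The outcome is named as an incidence, but the only recording rule gives an early score close to a point prevalence. First symptoms after that score are left out, and the reported figure understates postoperative incidence to the extent that such symptoms occur.

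Neither the amount nor any effect on the between-arm comparison can be determined, because the documents give no emesis rates, onset pattern or PCA start time. The conclusion assumes that the 0-3 score is the source of the outcome. The primary pain outcome and the sample size are untouched. This is worth correcting because the change is small and makes the reported incidence mean what its name says. It will not make the comparison decisive.

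**What to change.** 1. Record the 0-3 score immediately after surgery and at 2 and 6 hours. At each later contact, enter the worst symptom since the previous one. Add the 4-hour or 15-minute contact once the two pain lists have been reconciled.
2. Under Secondary outcome parameters, define the outcome as any score of 1 or more over 0-6 hours, using each patient's worst score. Also report any score of 3, and keep the immediate score as a descriptive value.
3. Extend the window to 24 hours only if a patient contact already takes place when the 24-hour morphine total is read.
4. If later scoring is not feasible, rename the outcome as the immediate postoperative nausea and vomiting score.

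The cost is two extra entries per patient at contacts already planned, made by the blinded colleagues who collect the postoperative observations. Some recall error is to be expected, mainly between 2 and 6 hours. The protocol ties ondansetron to this score, so the text must state how the added entries relate to that link. No clinical rule is proposed here. Renaming the outcome adds no data collection.
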